## METHODS

Study design and protocol (informed consent in Appendix 1):

Prospective multicenter, controlled, randomized study.

Inclusion criteria: Patients > 18 years who meet weaning criteria (see below) after at least 24 hours of MV, and with informed consent signed by them or their next of kind.

Exclusion criteria: tracheostomy, do-not-reintubate orders, decision of the responsible physician (e.g., due to a preference for a particular weaning technique according to the underlying pathology), absence of informed consent, mental incapacity without legal representation.

Weaning criteria:

- Suitable cough (Ability to raise secretions to the endotracheal tube) (or  $PiMax > -15$  cmH2O).
- Absence of excessive secretions (<3 aspirations in the last 8 hours).
- Resolution or improvement of the pathology that led to intubation.
- Clinical stability (HR <140 bpm, SBP 90-160, without vasopressors or at minimum doses).
- Adequate oxygenation (SatO2 > 90% with FiO2 <0.4).
- Adequate ventilatory mechanics (RR <35 rpm, MIP <-20 cmH2O, Vt > 5 ml / kg, VC > 10 ml/ kg, RR / VT <100 rpm/l).
- Confident awareness level (Glasgow Coma Scale > 13).

Prior to the SBT, attending physicians will state whether they intend to apply prophylactic post-extubation high flow nasal cannula or non-invasive mechanical ventilation. Patients will be in Fowler position (seated at 45° angle), the tracheal secretions will be suctioned before SBT, and FiO2 will remain at the same level than when receiving MV. A cuff-leak test will be performed by deflating the cuff and looking at the difference between inspired and expired volumes.

Patients will be randomized to two weaning strategies (see statistical analysis for more information):

- Standard: PSV 8 cmH2O, PEEP 0 cmH2O for 30 minutes and, when successful, followed by extubation with continuous suctioning.
- Lung volume preservation: PSV 8 cmH2O, PEEP 5 cmH2O for 30 minutes and, when successful, followed by direct extubation without suctioning.

Other components of standard treatment of patients (physiotherapy, nutrition, hydration...) will remain at the discretion of attending physicians and local protocols. During the SBT, if the patient meets any of the criteria for failure (see below), MV will be reconnected with the same parameters as prior to the SBT.

Failure of SBT will be defined as:

- Subjective indexes:

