***Variables (CRF in Appendix 2):***

Demographic variables: Age, sex, weight, height. Comorbidities: heart disease, neurological disease, COPD, diabetes, cancer, chronic renal insufficiency, liver disease. Variables at admission and during SBT: Diagnosis at admission to the ICU, reason for intubation, APACHE II on admission and on the day of extubation, hospital admission date, and date of admission to the ICU.

At the beginning and at the end of the SBT: FiO2, respiratory rate, SaO2, tidal volume during the SBT. If blood gas analysis is performed prior to extubation: PaO2, PaCO2, pH, bicarbonate and base excess.

Outcome variables: Respiratory failure at 72 hours post-extubation and criteria. If blood gas analysis is performed after failure: PaO2, PaCO2, pH, bicarbonate and base excess.

In cases with respiratory failure and rescue NIV, maximum FiO2, IPAP, and maximum EPAP, as well as the hours of application, will be recorded.

If post-extubation high-flow nasal cannula is used, maximum FiO2 and flow will be recorded.

If the patient is reintubated within 72 hours, the time and cause of reintubation will be recorded.

The CRF will be recorded in the RedCap® platform.

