## STATISTICAL ANALYSIS AND CALCULATION OF SAMPLE SIZE

Considering a basal extubation success of 82%, estimating an increase in absolute extubation success rate of 5%, with an alpha error of 0.05 and a power of 80%, requires a sample size of 822 patients in each group. With the participating hospitals, this sample will be obtained in 12 to 18 months, according to the recruitment rates. Recruitment will begin in October 2022 and will end in May 2024.

The randomization will be carried out with the built -in tool of the REDCAP® platform with computerized random numbers tables and patient N blocks for each hospital (researchers will be blinded on this data). Each participating center will have two different Redcap® profiles. The "recruiter" will have access only to the randomization tool and will not have access to data entry (only one recruiter per center). Another profile will be the "researcher" that will have access to randomization and data entry (as many profiles as researchers for each center). Researchers will have access to the data of their centers, but cannot access the data of other centers. Only trial coordinators will have access to data from all centers.

Before analyzing the results and managing the database, we will check the database to detect errors such as variables or repeated patients, or the lack of values in the

variables through the statistical computer program SPSS version 22® and R-Studio version 3.0®.

When half of the sample has been recruited, a preliminary analysis will be conducted to identify the trend of the results in the primary outcome. If significant ( $p < 0.005$ ) results have been obtained in one of the two randomization groups at that point, the inclusion of patients will be stopped. This analysis will be blinded to investigators.

In the descriptive analysis, quantitative variables will be expressed as means and standard deviations (if normally distributed) and as medians and interquartile ranges (if non-normally distributed). Qualitative variables will be expressed as frequencies and percentages.

Quantitative variables will be compared by Student's t-tests and qualitative variables by chi-square or Fisher's test.

Survival analyses for respiratory failure at 72 hours, reintubation at 72 hours, and mortality at 3 months will be performed with Kaplan-Meier curves with logarithmic rank test for comparison between both groups.

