To identify causes of extubation failure, multivariate by logistic regression will be performed, adjusting for confusion factors such as type of pathology, blood gas analysis variables, and center.

The results will be analyzed in three ways:

1. Patients who failed the SBT.
2. Patients who passed the SBT:
  - a. Successful extubation
  - b. Reintubation within 72 hours.

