### INCLUSION CRITERIA FOR PARTICIPATING CENTERS

Before starting the study, a technical and competence evaluation of the centres participating in the ultrasound substudy will be carried out (at least 15 have shown interest) within the 34 participating centres in the RCT *Preserving lung volume at Extubation*. At least one collaborator will be designated in charge of the centre with accredited experience in lung ultrasound according to the recommendations of the APECHO study (xx) through a course endorsed by the scientific society of intensive care or ultrasound, or at least 25 complete examinations supervised by an expert, who will supervise the personnel of their competent unit for the acquisition of the quality ultrasound images.

Availability of suitable convex and linear probes with the ability to record 3 to 10 seconds video clips.

Ability to download ultrasound images in DICOM format.

Passing the trial period of sending at least 5 scans (all LUSm windows, diaphragmatic and intercostal thickening of 5 different patients) to test that meet the described requirements and can be technically correctly interpreted by an independent observer.

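### Randomisation is blocked within hospital but no stated comparison of the arms uses hospital; stratifying the tests by hospital is a small gain in power at no cost

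*Combined protocol and SAP*

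**What the plan says.** All of the main trial's analysis text is in the section on statistical analysis and sample size.

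- **Allocation.** Randomisation uses "computerized random numbers tables and patient N blocks for each hospital". The block size is not disclosed.
- **Binary and continuous outcomes.** "Quantitative variables will be compared by Student's t-tests and qualitative variables by chi-square or Fisher's test". No separate test is named for the primary outcome, and none for the half-sample look with its stopping threshold of p<0.005.
- **Time-to-event outcomes.** Respiratory failure and reintubation at 72 hours and mortality at 3 months "will be performed with Kaplan-Meier curves with logarithmic rank test for comparison between both groups", with no strata.
- **Centre.** It appears once, in a logistic regression meant to identify causes of extubation failure, "adjusting for confusion factors such as type of pathology, blood gas analysis variables, and center". Treatment arm is not named as a term in that model.

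Two other places bear on the point. The Methods leave other components of care so that they "will remain at the discretion of attending physicians and local protocols". The ultrasound substudy, under inclusion criteria for centres, counts "34 participating centres" in the main trial.

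**The concern.** Blocking within hospital makes the arms nearly equal in size at every hospital. Differences in success rate between hospitals then cancel, or nearly cancel, out of the arm difference. A test that pools all hospitals into one 2×2 table does not know this. Its standard error still contains the between-hospital variation, so it is too large whenever hospitals differ. The test then rejects less often than its nominal 5% under the null and has less power than the design could deliver.

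Some variation between hospitals is plausible, since other care follows local practice and the plan itself lists centre as a confounder. What is at stake is a modest amount of power and precision that the allocation scheme has already provided. The validity of the trial is not in question. A lesser matter is that the primary test has to be inferred from a general rule offering two options, so a choice to stratify made after seeing data could be challenged.

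**Working it through.** **Inputs from the documents.** Control success 82% ("Considering a basal extubation success of 82" percent), a 5-point absolute increase, alpha 0.05, power 80%, 822 per group (1,644 in total), 34 hospitals, blocks within hospital.

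**Assumptions.** A two-sided test (not stated, but it reproduces the sample size); 1:1 allocation; block size 4, with 10 as a check; and the between-hospital spread, which the documents do not give and which is varied below.

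**Step 1: reproduce the plan's figure.** With p̄ = 0.845,

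n = [1.960·√(2·0.845·0.155) + 0.8416·√(0.82·0.18 + 0.87·0.13)]² / 0.05² = (1.0031 + 0.4297)² / 0.0025 = 821.2, so 822 per group.

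Power at 822 is 80.04%. The plan's figure is right.

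**Step 2: analytic size of the effect.** Let ICC be the share of outcome variance that lies between hospitals. Under blocking, the true variance of the arm difference is about (1 − ICC) times the variance the unstratified test uses.

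- Type I error of the unstratified test: 2·[1 − Φ(1.96/√(1 − ICC))]. At ICC 0.02 this is 2·[1 − Φ(1.980)] = 4.77%.
- Power at ICC 0.02. The null SE used by the chi-square is √(0.26195/822) = 0.01785. The true SE is √(0.98·0.2607/822) = 0.01763. Unstratified: Φ[(0.05 − 1.96·0.01785)/0.01763] = 80.3%. Stratified, with null SE 0.01785·√0.98 = 0.01767: Φ[(0.05 − 1.96·0.01767)/0.01763] = 80.8%.

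The analytic gains at ICC 0, 0.01, 0.02, 0.05 and 0.10 are 0, +0.3, +0.5, +1.4 and +2.7 power points.

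**Step 3: simulation.** 34 hospitals of unequal size (Dirichlet(2)), permuted blocks of 4 with the last one incomplete, normal hospital effects on the logit scale, marginal success held at 82% and 87%, rejection at |z| > 1.96. There were 30,000 trials per power scenario and 20,000 per null scenario.

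| Logit SD (assumed) | 95% range of control hospitals | Chi-square power | CMH power | Gain (points) | Chi-square type I error |
|---|---|---|---|---|---|
| 0 | none | 80.1% | 80.1% | 0 | not listed |
| 0.3 | 72–89% | 80.2% | 80.5% | +0.3 | 4.9% |
| 0.5 | 65–93% | 80.0% | 80.8% | +0.75 | 4.5% |
| 0.7 | 57–95% | 80.8% | 82.3% | +1.6 | 4.3% |
| 0.9 | 50–97% | 81.1% | 83.6% | +2.5 | 4.0% |

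Gains were taken before rounding. CMH type I error was 4.9–5.0%. A logit SD of 0.28, 0.39, 0.63 and 0.91 corresponds to ICC 0.01, 0.02, 0.05 and 0.10, so Steps 2 and 3 agree.

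**Step 4: sensitivity.** With blocks of 10 the gains at SD 0.3, 0.5, 0.7 and 0.9 are +0.2, +0.7, +1.5 and +2.6. With 20 hospitals the gains at SD 0.3, 0.5 and 0.7 are +0.3, +0.8 and +1.6. On average 6.7 of the 34 hospitals had fewer than 20 patients at full sample; pooling them changed CMH power by 0.1 point or less.

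**Step 5: what SD 0.5 is worth.** A gain of 0.75 points moves power from 80.04% to 80.79%, that is, from z = 0.843 to z = 0.870. The equivalent increase in sample size is (2.830/2.803)² − 1 ≈ 2%, or about 30 of 1,644 patients. The mean 95% interval for the risk difference narrows from 6.97 to 6.87 points.

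**The case against.** **The gain is small and its size is assumed.** Both are true. At SD 0.3 to 0.5 it is under one power point, and no likely conclusion of the trial turns on it. The protocol also standardises the weaning criteria, the breathing-test settings and the failure criteria, which argues against the widest spreads. The rows at SD 0.7 and 0.9 show the range and are not a forecast.

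**Stratifying removes slack that offsets the interim look.** The plan looks at half the sample at p<0.005 and states no reduced final alpha. With a final test at 0.05, a test of exact size has an overall two-sided error of 5.19%. The conservative unstratified test has about 5.1% at ICC 0.01 and 4.9% at ICC 0.02. The arithmetic stands, but the excess over 5% comes from the unadjusted look. An unknown amount of conservatism is not a way to control it.

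**At the half-sample look many hospitals are small.** With the same size distribution, about 16 of 34 hospitals would have fewer than 20 of the 822 patients, holding about 175 between them. A simulation of that look (20,000 trials per scenario, threshold 0.005, those hospitals pooled) gave power of 20.3% for chi-square against 20.2% for pooled CMH at SD 0, 20.6% against 21.0% at SD 0.3, and 19.8% against 20.6% at SD 0.5. Pooling does not make the stratified test worse than the planned one. It does mean that the strata can differ between the two looks, so the rule must be written down.

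**The log-rank tests were not quantified.** This stands. The documents give no event rates for reintubation or mortality, and the figures above concern extubation success only.

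**Centre is not wholly absent.** Also true, but the regression that uses it is aimed at causes of failure. It also adjusts for blood gases, which are recorded only if taken, at the end of the breathing test or after failure. It cannot serve as the comparison of the arms.

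**Conclusion.** The point holds as a minor efficiency improvement. The unstratified test is valid, erring if anything on the conservative side, and the sample size of 822 per group stands. Ignoring hospital forgoes about 0.3 to 0.75 power points if the between-hospital logit SD is 0.3 to 0.5, more if hospitals differ more, and nothing material if they do not differ.

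The direction follows from blocking within hospital and does not depend on the assumptions. The size depends on the between-hospital spread and, slightly, on the block size and the distribution of hospital sizes, none of which the documents give. The benefit for the log-rank tests is expected on the same reasoning but has not been measured.

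**What to change.** In the section on statistical analysis and sample size:

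1. Name the primary test of extubation success: a CMH test stratified by hospital, reported with the Mantel-Haenszel risk difference and its 95% confidence interval. Use the same test at the half-sample look.
2. State in advance how very small hospitals are handled at each look, for example by pooling those with fewer than 20 randomised patients at the time of that analysis into one stratum, decided without sight of outcomes. The threshold of 20 is only an example.
3. Stratify the 72-hour and 3-month log-rank tests by hospital. This is for consistency with the allocation; its gain is unquantified.
4. If a supporting covariate-adjusted comparison of the arms is added, restrict it to variables fixed before randomisation. The case report form records "APACHE II on admission and on the day of extubation"; only the admission value is sure to qualify. COPD and reason for intubation also would.

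The regression on causes of extubation failure can stay as it is. The cost is SAP wording and a few lines of code, settled before any outcome comparison is seen. No extra data or patients are needed, and the sample size does not change.

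### No covariate-adjusted comparison of the arms is planned for extubation success; the unadjusted test is valid, but extra precision from baseline data already collected is forgone

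*Combined protocol and SAP*

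**What the plan says.** The primary objective of the main protocol is the rate of successful extubation under two strategies, which is a binary outcome. The section on statistical analysis and sample size assigns no test to that outcome by name. It gives a rule by type of variable: "Quantitative variables will be compared by Student's t-tests and qualitative variables by chi-square or Fisher's test". The sample size is an ordinary two-proportion calculation and "requires a sample size of 822 patients in each group".

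The same section adds: "Survival analyses for respiratory failure at 72 hours, reintubation at 72 hours, and mortality at 3 months will be performed with Kaplan-Meier curves", compared by log-rank test. No covariates are mentioned there either.

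One multivariable model is planned, a logistic regression to identify causes of extubation failure, "adjusting for confusion factors such as type of pathology, blood gas analysis variables, and center". It is not described as estimating the difference between arms.

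The Variables section lists data fixed before randomisation: "Demographic variables: Age, sex, weight, height. Comorbidities: heart disease, neurological disease, COPD, diabetes, cancer, chronic renal insufficiency, liver disease". It also lists admission diagnosis, reason for intubation and APACHE II on admission. Randomisation is in blocks within each hospital.

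**The concern.** In a randomised trial with a binary outcome, adjusting for baseline predictors and standardising back to a risk difference keeps the estimand the trial was sized on, an absolute difference in success. It usually reduces the variance, and it corrects for chance imbalance in the adjusted covariates. The plan holds suitable variables and does not use them for the comparison of arms.

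Two features make this worth raising. First, the sample size has no stated allowance for loss, and the ethics section says that data are deleted when a patient or representative asks to be withdrawn from the database. Any such loss takes power slightly below 80%. Second, the only adjusted model written down includes blood gases. The Methods section makes the gas analysis at the end of the breathing test optional, and it comes after randomisation, because the test itself is what is randomised. If an adjusted effect were wanted later, the choices would be covariates picked after seeing the data or a set that includes optional post-randomisation measurements.

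**Working it through.** **1. Reproduce the plan's figure.** Inputs from the sample-size paragraph: success 82% vs 87%, alpha 0.05, power 80%. Sidedness is not stated.

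n per group = [z(0.975)·√(2·0.845·0.155) + z(0.80)·√(0.82·0.18 + 0.87·0.13)]² / 0.05²
= (1.960·0.5118 + 0.8416·0.5106)² / 0.0025 = 821.2, so 822.

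This matches. A one-sided test would give 647, so the plan is two-sided without continuity correction. Power at 822 per group = Φ[(0.05·√822 − 1.960·0.5118) / 0.5106] = Φ(0.843) = 80.04%.

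**2. Gain from adjustment (assumed prognostic strength).** The documents give no figure for how well the baseline variables predict extubation outcome, so the AUC is an assumption shown over a range. Pooled planned failure is (18% + 13%)/2 = 15.5%. For a normally distributed linear predictor in a logistic model with mean failure 15.5%, the spread is solved to give each AUC. Then R² = Var(pᵢ)/(0.155·0.845), the effective size is 822/(1 − R²) per group, and the power formula above is reapplied. The equivalent number of extra patients is 1,644/(1 − R²) − 1,644.

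| Assumed AUC | R² | Power at 822 per group | Equivalent extra patients |
|---|---|---|---|
| none | 0 | 80.0% | 0 |
| 0.60 | 1.7% | 80.7% | about 28 |
| 0.65 | 4.0% | 81.6% | about 68 |
| 0.70 | 7.4% | 83.0% | about 131 |
| 0.75 | 12.2% | 84.9% | about 228 |

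**3. Check by simulation.** 4,000 trials per scenario were simulated with 822 per arm, marginal rates of 82% and 87%, and one baseline score. The pooled z test (equivalent to the chi-square) was compared with the Wald test for arm in a logistic regression on arm and score. Power, unadjusted vs adjusted, was:
- AUC 0.60: 80.6% vs 81.2%
- AUC 0.65: 81.7% vs 82.2%
- AUC 0.70: 81.0% vs 83.1%
- AUC 0.75: 81.0% vs 85.1%

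The Monte Carlo standard error of each figure is about 0.6 points. With no treatment effect, rejection rates were 4.6% to 5.5% for both tests.

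**4. Chance imbalance.** The standard deviation of the between-arm difference in a standardised score is √(2/822) = 0.049, so 95% of trials lie within 1.96·0.049 = 0.097 SD. The matching shift in the success difference is about 0.097·√(R²·0.155·0.845). That is 0.5, 0.7, 0.95 and 1.2 percentage points at AUC 0.60, 0.65, 0.70 and 0.75, against a target of 5 points.

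**5. Room for the model.** Expected failures are 0.155·1,644 ≈ 255, enough for a short list of patient covariates. The ultrasound substudy protocol counts 34 centres in the main trial. That is 255/34 ≈ 7.5 failures per centre at the end, and 0.155·822/34 ≈ 3.7 at the halfway look, too few for a separate term for every small centre.

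**The case against.** The strongest reply is that the design and its evident test agree. The trial was sized for an unadjusted comparison and keeps its 80% power and its type I error. A reader might infer that power is lost or that the chi-square is wrong. The documents support neither, and having no margin above target is true of any trial sized to its target. This part of the objection stands in full.

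A reader might also take the baseline variables to be strong predictors. No section says so. Most are admission-time variables, while the trial enrols patients ventilated for at least 24 hours who have met readiness criteria, so their value in that selected group may be modest. At AUC 0.60 to 0.65 the gain is 0.7 to 1.6 points by formula and about half a point by simulation. That stands too.

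Nor does the causes-of-failure model show that the plan regards age, APACHE II or comorbidities as drivers of failure. Its open list names only pathology, blood gases and centre.

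Finally, adjustment does not remove chance imbalance in general. It acts only on covariates in the model, and at this size the expected shifts are small.

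What survives is that no adjusted comparison of the arms is prespecified, that even the blocking factor is absent from the comparison, and that usable covariates are already collected.

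**Conclusion.** The point holds as an efficiency and prespecification improvement, not as an error. The planned comparisons of the arms on extubation success and the 72-hour failure outcomes are unadjusted. That chi-square or Fisher applies to the primary outcome is inferred from a generic rule, because the plan assigns it no test by name.

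The unadjusted analysis is valid at 80.04% power. Under assumed AUCs of 0.60 to 0.75, adjustment would add about 0.7 to 4.9 points of power and correct a shift that in 95% of trials is no more than about 0.5 to 1.2 points. The size of the benefit rests wholly on the assumed AUC. The case for naming the covariates in advance does not.

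**What to change.** In the statistical analysis section of the main protocol:

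- Name the primary analysis: a logistic regression of successful extubation on arm, hospital and a short fixed list of pre-randomisation covariates, for example age, admission APACHE II, COPD, heart disease, neurological disease and reason for intubation.
- Include hospital because it is the blocking factor, with small centres pooled by a stated rule or hospital as a random effect.
- Report a standardised (g-computation) risk difference with 95% CI, which stays on the scale of the 5-point design effect.
- Exclude blood gases, breathing-test readings and APACHE II on the day of extubation, which are or may be measured after randomisation. The physician's stated intention to use prophylactic support could be added only if it is confirmed to be recorded before allocation.
- Use the same model at the halfway look, with the p < 0.005 threshold unchanged.
- State a simple rule for missing covariates, so that no patient is dropped for a missing baseline value.
- Keep the unadjusted chi-square as a sensitivity analysis, and leave the sample size at 822 per group, since the gain is assumed.

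The cost is plan wording, to be fixed before any comparison by arm, and modest extra programming. No new data and no additional patients are needed.
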